### Double Blind Treatment Period (V4 to V8, 24 weeks)

Following completion of the lead-in phase, eligible patients will enter the 24-week double-blind treatment phase. The dose of Oral Anti-diabetic Drugs (OADs), insulin, anti-hypertensive drugs, lipid lowering drugs and anti-platelet drugs should be kept constant throughout the 24-week double-blind treatment period.

If dose of OADs and insulin is reduced according to the investigator discretion, patient should still continue in the study with double blind treatment and the dose changes must be recorded in the appropriate sections of the electronic CRF.

### Rescue Medication Due to Lack of Glycemic Control in the Treatment Period

Patients with lack of glycemic control during the 24-week treatment period may be eligible to receive open-label rescue medication in addition to their blinded treatment in order to treat ongoing hyperglycemia. Patients may receive open-label rescue medication added on to, but not as a replacement for, their current study drug regimen. Rescue medication in the study refers to any approved, appropriate anti-diabetic agent, except SGLT2-inhibitors, for which there is either initiation or upward titration, in accordance with the approved label and conventional standards of care. Open-label rescue medication is to be titrated as needed to obtain adequate glycemic control. Patients who received a first rescue medication, who subsequently fulfil lack of glycemic control criteria, may have other rescue medications added or substituted, according to Investigator judgment.

During the 24-week double-blind treatment period, all rescue decisions will be based on central laboratory FPG and confirmatory FPG results. If patients meet the protocol-specified glycemic criteria based on FPG (see [Table 4](#) below), they will be recommended for open-label rescue medication.

Between scheduled visits, the patients will be asked to check their blood glucose if they develop symptoms suggestive of hyperglycemia. The sections and tables listed below define the lack of glycemic control criteria. Glucometers will be provided by AstraZeneca. The patients will receive instructions for the use of the glucometer according to the manufacturer's instructions. Patients will be instructed to contact the investigator if they experience a hyperglycemic event in order to schedule an extra visit for central laboratory FPG and if needed, a confirmatory, repeat FPG.

**Table 4 Lack of Glycemic Control Criteria for Initiation of Open-Label Rescue Medication**

Visit Label	Central Laboratory FPG
From Week 4 (Visit 6) to Week 12 (Visit 7) (excluding Week 12)	FPG >240 mg/dL (13.3 mmol/L)
From Week 12 (Visit 7) to Week 24 (Visit 8) (excluding Week 24)	FPG >200 mg/dL (11.1 mmol/L)

Patients with a central laboratory FPG value meeting the lack of glycemic control criterion at a pre-specified visit will be scheduled for a follow-up visit (within 3 - 5 days) to obtain a second central laboratory FPG value and review the patient's glucose meter readings. If the repeat central laboratory FPG value still meets the criterion, the patient will receive rescue medication.

Irrespective of study visit number, patients who meet rescue criteria in the treatment period must first complete the Week 24 visit's procedures before receipt of open-label anti-diabetic rescue medication to ensure that important study endpoint measurements are collected.

Following completion of the Week 24 “Rescue” visit, rescued patients will be administered open-label rescue medication in addition to their blinded study drug. Rescued patients will then continue in the treatment period according to their original visit schedule. Patients who received a first open-label anti-diabetic rescue medication, who subsequently fulfill lack of glycemic control criteria described in the [Table 4](#) above, may have other rescue medications added or substituted, according to Investigator judgment, without repetition of rescue visits.

Patients with a central laboratory FPG value >200 mg/dL (11.1 mmol/L) at Week 24 (Visit 8), will not be considered as rescued for efficacy analysis.

### **Follow-up Period (V8 to V9, 3 weeks)**

After completion of the treatment period, patients will enter a 3-week safety follow-up period without study drug. At the follow-up visit (Visit 9 (FU)) any changes in physical signs, renal function (*i.e.*, changes in eGFR), symptoms or laboratory parameters that may be related to dapagliflozin will be evaluated. Patients who discontinue study drug will remain in the study for follow-up and complete all scheduled study visits through Week 27. At the time of discontinuation the Week 24 procedures will be performed. Patients will not receive double-blind study drug during this follow-up period, but will complete all scheduled study visits and procedures.

The total planned study duration from Visit 1 to the safety follow-up (Visit 9) will be 33 weeks.

## **1.3 Treatment Group Assignment**

The randomization codes will be computer generated by AstraZeneca R&D using the AZ Randomization system (AZRand) and loaded into the IVRS/IWRS database. Randomization codes will be generated to ensure approximate balance (1:1) between the two treatment arms (dapagliflozin 10 mg or matching placebo, once daily).

Randomization will be done via IVRS/IWRS at Visit 4. The IVRS/IWRS will allocate randomization codes sequentially through central randomization as patients become eligible for randomization.

Randomization will be stratified by pre-enrolment anti-hyperglycemic therapy. The following 5 strata will be defined:

1. Insulin-based regimen: Patients receiving insulin alone or in combination with any other anti-hyperglycemic medication
2. Metformin-based regimen: Patients receiving metformin alone or in combination with any other anti-hyperglycemic medication except insulin
3. SU-based regimen: Patients receiving a SU alone or in combination with any other anti-hyperglycemic medication except insulin and metformin

4. TZD-based regimen: Patients receiving a TZD alone or in combination with any other anti-hyperglycemic medication except insulin, metformin, or a SU
5. Other regimen: Patients receiving either any anti-hyperglycemic medication(s) not described by strata 1-4, or no background anti-hyperglycemic medication.

For each patient randomized the IVRS/IWRS will provide the investigator with a unique Kit ID number matching the treatment arm assigned to the patient. Following randomization, the first dose of study drug will be administered to the patient after completion of study visit procedures. At randomization and subsequent dispensing visit the patient should always be provided medication with the Kit ID(s) allocated by the IVRS/IWRS. If a patient receives the incorrect randomized treatment at any time during the study, the centre must immediately notify the AstraZeneca representative and IVRS/IWRS contact and this must be corrected as soon as discovered after discussing with study physician.

#### **1.4 Sample Size Estimate**

The primary endpoint is the change from baseline in HbA1c at Week 24. From post-hoc results of similar clinical studies (Study MB102029, Study D1690C00018, and Study D1690C00019) when patients meeting eGFR entry criteria like those in this current study were selected, the mean placebo-corrected change from baseline in HbA1c after 24 weeks of treatment for the current study is estimated to be -0.3% for dapagliflozin 10 mg.

Assuming a common standard deviation (SD) of 0.9% in the primary endpoint, 143 patients per treatment group with both baseline and at least one post-baseline HbA1c measurement will provide 80% power to detect a treatment difference of 0.3% in the primary endpoint at a two-sided significance level =0.05, using a two-sample t-test. Assuming that 5% of randomized patients fail to qualify for inclusion in the full analysis set due to missing baseline and/or all post-randomization values for this primary endpoint, a total of 302 randomized patients (151 per treatment group) are needed for the study.

## **2. ANALYSIS SETS**

### **2.1 Definition of Analysis Sets**

#### **2.1.1 Enrolled Patients Set**

The Enrolled Patients Data Set includes data collected from all patients who signed informed consent. For this study, per change to the inclusion/exclusion criteria in Amendment 3, patients can be re-enrolled a single time, but they cannot be re-randomized. Re-enrolled patients will be assigned new Ecode and will be counted only once in the Enrolled Patients Data Set.

#### **2.1.2 Lead-in Analysis Set**

For the summary of patients enrolled in the lead-in period, all patients with an E-code and who took at least one dose of lead-in medication (Placebo) will be included in the analysis set.

### **2.1.3 Randomized Analysis Set**

For the summary of demographic and baseline characteristics, all patients assigned a randomization code by the IVRS/IWRS system will be included in the analysis set.

### **2.1.4 Full Analysis Set**

The primary efficacy analysis will be performed on the Full Analysis Set (FAS) which will consist of all randomized patients who took at least one dose of double-blind study drug and have a non-missing baseline value and at least one post-baseline on any of the efficacy variables (HbA1c, total weight, FPG and SBP).

When the Full Analysis Set is used, patients will be presented in the treatment group to which they were randomized regardless of the treatment actually received.

### **2.1.5 Per Protocol (PP) Analysis Set**

The PP Analysis Set is a subset of the Full Analysis Set and will consist of patients who do not deviate from the terms specified in Appendix A (important protocol deviation), which may affect the study outcome significantly and interpretation of the study results. All decisions to exclude patients from the primary data set will be made prior to the unblinding of the study.

The PP Analysis set will only be applied if the PP Analysis set has a minimum of 10% fewer patients than the Full Analysis Set due to important protocol deviations. In that case, only the primary efficacy endpoint of change from baseline in HbA1c will be analyzed using the PP Analysis set. Demographics, and baseline diabetes characteristics will be summarized using the PP Analysis set if necessary.

### **2.1.6 Safety Analysis Set**

The Safety Analysis Data Set will consist of all patients who received at least one dose of double-blind study drug during the double-blind treatment period. The Safety Analysis Data Set will include any patient who accidentally received double-blind study drug but was not randomized in the study.

All analyses using the Safety Analysis Data Set will be presented by randomized treatment group, except in cases where information was available which indicated that a patient received a different treatment for the entire course of their participation in the double-blind treatment period of the study. In this case, the safety data for those patients will be presented by the treatment actually received. In case a patient never received the treatment as assigned by randomization, then the safety data for that patient will be presented by the first treatment received.

## **2.2 Blinding and Unblinding**

### **2.2.1 Blinding**

The investigator, AstraZeneca personnel, and patients will remain blinded to treatment allocation throughout the entire study period. The database used for the analysis of the double-

blind data of the study will be locked after all patients have terminated the study. In order to protect the integrity of the treatment period of the study, the patients and investigators will not have access to the individual treatment assignments until the study has completed.

Unless otherwise specified, to maintain integrity of the study, HbA1c and urinary glucose values will be masked to AZ as well as on laboratory reports to investigators during the double-blind study period. See protocol for further details.

### **2.2.2 Unblinding**

Blinding is critical to the integrity of this clinical trial. However, in the event of a medical emergency or pregnancy, during which knowledge of the identity of the investigational product is critical to the patient's management, procedures are in place to have the blind broken for an individual patient. A separate procedure is in place for unblinding in case of expedited safety reporting to regulatory authorities.

Unmasked HbA1c and urinary glucose values will be transferred from the Central Lab between “Clean File” and “Database Lock”. Unblinding of treatment data will also occur after “Clean File” and before “Database Lock”. The locked database will be unblinded for reporting purposes.

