3.6 Methods for ensuring blinding

The study has a single-blind placebo lead-in period of 4 weeks from Visit 2, where patients will be blinded to treatment. Other members at AstraZeneca, investigational centres or any Contract Research Organization (CRO) handling data will be aware of the placebo treatment during this period.

The study will be conducted in a double-blind fashion. The dapagliflozin 10 mg tablet and its matching placebo will be identical in size, colour, smell, taste, packaging and labelling.

Until the completion of the 24-week randomized treatment period, no member of the study team at AstraZeneca, at the investigational centres or any CRO handling data will have access to the randomization scheme, with the exception of AstraZeneca personnel generating the randomization scheme as well as relevant persons at Pharmaceutical Development Supply Chain at AstraZeneca or their designee, where the information is needed to package study drug, the Patient Safety data entry site and the CRO companies providing the IVRS/IWRS and

carrying out the packaging and labelling of investigational products. Patients and investigators will remain blinded past the 24-week randomized treatment period.

The treatment codes and results will be kept strictly within AstraZeneca to safeguard the integrity of the blind of the investigators and patients, and hence to minimize any possible bias in data handling.

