7.8 Post Study Access to Study Treatment – Not Applicable

8. STATISTICAL ANALYSES BY ASTRAZENECA

8.1 Statistical considerations

- All personnel involved with the analysis of the study will remain blinded until database lock and protocol violators identified.
- Analyses will be performed by AstraZeneca or its representatives.
- Refer to SAP for details.
- All personnel involved with the analysis of the study will remain blinded until database lock and protocol violators are identified. Analyses will be performed by AstraZeneca or its representatives.

A comprehensive Statistical Analysis Plan (SAP) will be prepared prior to first patient randomized and any subsequent amendments will be documented, with final amendments completed prior to unblinding of the data (this is the expectation for the pivotal studies).

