9.4 Data management by AstraZeneca or delegate

Data management will be performed by **CCI** the AZ Data Management Centre, according to the Data Management Plan.

Data will be entered into the WBDC system Rave at the study site. Trained site staff will be entering the data as specified in the protocol and according to the eCRF instructions. Data entered into the WBDC system will be immediately saved to a central database and changes tracked to provide an audit trail. The data will then be Source Data Verified, reviewed, queried and updated as needed

AEs and medical/surgical history will be classified according to the terminology of the latest version the MedDRA. Medications will be classified according to the AstraZeneca Drug Dictionary. All coding will be performed by the Medical Coding Team at the Data Management Centre.

The PI is responsible for signing the eCRF and this may be delegated to a trained Investigator.

The data will be validated as defined in the Data Management Plan. Quality control procedures will be applied to each stage of data handling to ensure that all data are reliable and have been processed correctly. The Data Management Plan will also clarify the roles and

responsibilities of the various functions and personnel involved in the data management process.

When all data have been coded, validated, signed and locked, clean file will be declared. Any treatment revealing data may thereafter be added and the final database will be locked. A copy of the eCRF will be archived at the study site when the study is completed.

Serious Adverse Event (SAE) Reconciliation

SAE reconciliation reports are produced and reconciled with the Patient Safety database and/or the investigational site.

Data associated with human biological samples

Data associated with biological samples will be transferred from laboratory(ies) internal or external to AstraZeneca.

Management of external data

Data Management determines the format of the data to be received from external vendors and coordinates the flow of data to the clinical database. Data Management will assure that the data collection tool for IVRS are tested and validated. External data reconciliation will be done with the clinical database as defined in the Data Management Plan.

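### Does the SAP allow treatment codes to be released before the primary-endpoint HbA1c values are final?

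*SAP*

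**What the plan says.** Four places bear on the order of events at the end of the study.

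- **SAP 2.2.2 (Unblinding).** "Unmasked HbA1c and urinary glucose values will be transferred from the Central Lab between" Clean File and Database Lock. The next sentence reads "Unblinding of treatment data will also occur after “Clean File” and before “Database Lock". The section closes by saying that the locked database is unblinded for reporting. It names no recipient of the codes.
- **Protocol 8.1 (Statistical considerations).** "All personnel involved with the analysis of the study will remain blinded until database lock and protocol violators" have been identified. SAP amendments are allowed, "with final amendments completed prior to unblinding of the data".
- **Protocol 9.4 (Data management).** "When all data have been coded, validated, signed and locked, clean file will be declared". Then: "Any treatment revealing data may thereafter be added and the final database will be locked". On data from outside vendors: "External data reconciliation will be done with the clinical database as defined in the Data Management Plan".
- **Protocol 3.6 (Methods for ensuring blinding).** "Until the completion of the 24-week randomized treatment period, no member of the study team at AstraZeneca", at the centres or at any contract research organisation handling data has access to the randomization scheme, apart from listed exceptions.

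HbA1c and urinary glucose are masked to the investigator and the sponsor during double-blind treatment (protocol 5.1, SAP 2.2.1). The HbA1c results at Weeks 4, 12 and 24 are the scheduled responses in the primary model.

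**The concern.** HbA1c is the primary endpoint, yet its unmasked values reach the sponsor only after Clean File, so the checks completed at Clean File cannot have covered them. SAP 2.2.2 links the HbA1c transfer and the code release only by saying that the second also happens in that interval. On that wording, someone could hold the codes while HbA1c results are still being received, queried or corrected in a database that is not finally locked.

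The wording also sits badly with protocol 8.1, where analysis staff stay blinded until lock. The other blinding texts do not close the gap. Protocol 3.6 bars access only until the 24-week period is complete. SAP 2.2.1 names the investigator, sponsor personnel and patients for the study period, but SAP 4.1 gives the analysis to a contract research organisation.

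If codes could influence how primary-endpoint values were cleaned, or which patients entered the primary model, the credibility of the main comparison would be at stake.

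**Working it through.** No arithmetic applies. The question is whether the texts, taken together, leave real room for codes to influence the primary endpoint.

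**1. Does the SAP depart from the protocol?** Protocol 9.4 gives this order: data validated and locked, clean file declared, treatment-revealing data added, final database locked. SAP 2.2.2 places code release between Clean File and Database Lock. These are the same interval. The SAP's amendment history (entry of 9 February 2017) calls the end of that interval the final database lock, which matches the second lock in protocol 9.4.

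**2. Is protocol 8.1 contradicted?** Protocol 9.4 uses the idea of locking twice: once for the data at clean file and once for the final database. Protocol 8.1 does not say which it means. Two ordinary readings reconcile the texts:

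- The lock in 8.1 is the one at clean file. Code release then comes after it.
- The lock in 8.1 is the final one. Codes are loaded by data management, and analysts see them only after that lock. The last sentence of SAP 2.2.2, under which the locked database is unblinded for reporting, fits this reading.

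Neither reading is written out, so 8.1 is ambiguous. It is not breached.

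**3. Could codes influence who is analysed?** Protocol 3.7 and SAP 4.1 forbid breaking the codes for the planned analyses until evaluability decisions are made and documented for each patient. SAP 4.1 adds assignment to analysis sets. SAP 2.1.5 and 2.3.1 say the same of per-protocol exclusions. There are two cases:

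- If those decisions need the HbA1c values, these rules already require the values to arrive before the codes. The order is then supplied by implication.
- If they do not, the order has no bearing on them. SAP 2.1.4 admits a patient to the Full Analysis Set on any of HbA1c, weight, FPG or SBP, and the last three are not masked.

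The further condition in protocol 8.5.1, a baseline and at least one post-baseline measurement, is mechanical: the value exists or it does not.

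**4. Could codes influence which HbA1c value is used?**

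| Step | Rule fixed in advance | Where |
|---|---|---|
| Measurement | Central laboratory | Protocol 5.1, 5.1.1 |
| Baseline | Last non-missing value up to first dose | SAP 4.1.1 |
| Visit assignment | Day windows: Week 4, 2–57; Week 12, 58–127; Week 24, 128 to end of period | SAP 4.3.1, Table 17 |
| Several values in a window | Nearest to target day, with tie rules | SAP 4.3.1 |
| After last dose | Used up to the 8th day | SAP 4.3.2 |
| After rescue | Excluded | SAP 4.1.3, 4.3.2 |
| Model | Fixed, with ordered back-ups | SAP 4.1.6.1 |

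The dosing and rescue dates that drive the cut-offs come from the case report form (SAP 4.2.5), which is validated before clean file. Rescue decisions rest on FPG, which is never masked. Once the laboratory file is loaded, the analysis value for each patient and visit follows by rule.

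**The case for a change.** The best case for a change is that it is cheap and concerns the primary endpoint. A few sentences could say that HbA1c and urinary glucose are loaded, reconciled and frozen before codes are released, and name who holds the codes. The clinical study report could then show that the primary data were final while still blinded. The SAP states sequence elsewhere: under SAP 4.2.7.1.6, the preferred-term lists for adverse events of special interest are finalised before both lock and unblinding. The primary endpoint has no matching sentence, and SAP section 6 declares no departure from the protocol.

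Part of this stands. SAP 2.2.2 states no order and no recipient, and protocol 8.1 does not say which lock it means. But low cost does not make a change necessary. No route has been shown by which a person holding codes could alter a central-laboratory result, or choose between results, under the rules tabulated above. Protocol 9.4 assigns reconciliation of external data to the Data Management Plan, which is the natural home for the load sequence. That plan is not among the documents, so silence in the SAP does not show that the order is unset.

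**Conclusion.** The concern does not call for a change. It is a gap in operational detail that a data-management and statistics team would fill sensibly: the laboratory file is loaded and reconciled, analysis sets are confirmed, and the codes are then merged. The SAP's interval agrees with protocol 9.4, protocol 8.1 can be reconciled in two ordinary ways, and the decisions most open to influence must already precede unblinding.

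No bias is shown, and the documents give no basis for sizing one. Sample size, power, significance level, model and analysis sets are untouched.

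This rests on two assumptions: that the evaluability rule in protocol 3.7 and SAP 4.1 is followed as written, and that reconciliation of the HbA1c transfer is a routine check of records against the laboratory file, not a review of individual results. If HbA1c results had been queried or excluded case by case after codes were available, the question would need to be reopened.
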